## **8. ADVERSE EVENT REPORTING**

### **8.1. Adverse Events**

All observed or volunteered AEs regardless of treatment group or suspected causal relationship to the investigational product(s) will be reported as described in the following sections.

For all AEs, the investigator must pursue and obtain information adequate both to determine the outcome of the AE and to assess whether it meets the criteria for classification as a serious adverse event (SAE) requiring immediate notification to Pfizer or its designated representative. For all AEs, sufficient information should be obtained by the investigator to determine the causality of the AE. The investigator is required to assess causality. Follow-up by the investigator may be required until the event or its sequelae resolve or stabilize at a level acceptable to the investigator, and Pfizer concurs with that assessment.

As part of ongoing safety reviews conducted by the sponsor, any nonserious AE that is determined by the sponsor to be serious will be reported by the sponsor as an SAE. To assist in the determination of case seriousness, further information may be requested from the investigator to provide clarity and understanding of the event in the context of the clinical study.

## **8.2. Reporting Period**

For SAEs, the active reporting period to Pfizer or its designated representative begins from the time that the subject provides informed consent, which is obtained prior to the subject's participation in the study, ie, prior to undergoing any study-related procedure and/or receiving investigational product, through and including 28 calendar days after the last administration of the investigational product.

Serious adverse events occurring to a subject after the active reporting period has ended should be reported to the sponsor if the investigator becomes aware of them; at a minimum, all SAEs that the investigator believes have at least a reasonable possibility of being related to investigational product are to be reported to the sponsor.

All adverse events (serious and nonserious) should be recorded on the Case Report Form (CRF) from the time the subject has taken at least 1 dose of investigational product through the subject's last visit.

## **8.3. Definition of an Adverse Event**

An AE is any untoward medical occurrence in a clinical investigation subject administered a product or medical device; the event need not necessarily have a causal relationship with the treatment or usage. Examples of AEs include but are not limited to:

- Abnormal test findings;
- Clinically significant symptoms and signs;
- Changes in physical examination findings;
- Hypersensitivity;
- Progression/worsening of underlying disease;
- Drug abuse;
- Drug dependency.

Additionally, they may include the signs or symptoms resulting from:

- Drug overdose;
- Drug withdrawal;
- Drug misuse;
- Drug interactions;
- Extravasation;

- Exposure during pregnancy (EDP);
- Exposure via breastfeeding;
- Medication error;
- Occupational exposure.

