### **8.13. Withdrawal Due to Adverse Events (See Also the Section on [Subject Withdrawal](#))**

Withdrawal due to AEs should be distinguished from withdrawal due to other causes, according to the definition of AE noted earlier, and recorded on the appropriate AE CRF page.

When a subject withdraws because of an SAE, the SAE must be reported in accordance with the reporting requirements defined below.

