### **9.1. Sample Size Determination**

A sample size of approximately 170 subjects (in the polyarticular cohort) will be enrolled in the open-label active treatment run-in phase to provide a power of approximately 90% or above to detect a difference in the rate of disease flares between study drug versus placebo in the double-blind phase, assuming a 54% to 65% response rate of ACR Pedi 30 from the run-in active treatment phase, a 2-sided 5% Type I error, and a true difference of at least 31% in flare rates between tofacitinib and placebo, with a placebo flare rate of 57%. Sample sizes for the polyarticular JIA categories were determined from a combination of prevalence data and precedents in the literature.

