### 6.6.1. Adverse Events

Adverse events will be summarized according to Pfizer data standards for each phase and for the entire study period while the subjects are exposed to tofacitinib. For the AE reported over entire study period, subjects randomized to the placebo group will only have their events and exposure during the open-label run-in phase counted, and there will be no comparisons performed.

For AE reporting for each phase, AEs will not be double counted across phases. Counting of AEs will be based on start date of AE. If the start date of an AE is in the open label phase, the end date of the AE in the double blind phase and severity of AE remained the same or became lower in both phases, then the AE will be counted in open label phase, not in the double blind phase. However, if the same AE started in the open label phase, and get worse in severity in the double blind phase, then the AE will be counted in both phases. In all these analyses attention will be restricted to assessments that occurred no more than 28 calendar days after the last dose of study drug.

AEs of special interest in double-blind phase and over the entire study period while the subjects are exposed to tofacitinib will be analyzed using incidence rates (IR), including death, serious infections, opportunistic infections excluding TB, tuberculosis, herpes zoster, malignancy excluding NMSC, NMSC (non-melanoma skin cancer), lymphoma, MACE (Major Adverse Cardiovascular Events), gastrointestinal perforations, and Interstitial Lung Disease (ILD). Adverse events of macrophage activation syndrome (MAS) will be analyzed using IR. The MAS, Deep vein thrombosis (DVT), and Pulmonary embolism (PE) will be listed.

CCI

CCI

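### Disease worsening is listed as an adverse event and flare is not exempted, so the efficacy outcome can enter the double-blind AE totals and make placebo look less safe

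*Protocol*

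**What the plan says.** - **AE definition.** Protocol 8.3 gives "Progression/worsening of underlying disease" among its examples of AEs. Protocol 8.1 requires every observed or volunteered AE to be reported, whatever the arm or suspected cause.
- **Flare.** Protocol 7.1.7 defines flare as a worsening of at least 30% in three or more of the six JIA core variables, with limits on improvement and minimum changes. It is confirmed by the Centralized Coordinating Center (CCC) and leads to discontinuation.
- **Withdrawal.** Protocol 6.9.1 gives flare its own withdrawal section. Protocol 8.13 states: "Withdrawal due to AEs should be distinguished from withdrawal due to other causes, according to the definition of AE noted earlier". That definition is the one in 8.3.
- **AE analysis.** SAP 6.6.1 states: "Adverse events will be summarized according to Pfizer data standards for each phase". Its readable text has no table that sets flare aside. SAP 6.6 pools polyarticular, ERA and PsA subjects and describes the safety summaries as descriptive.
- **Planning rates.** Protocol 9.1 assumes "a true difference of at least 31% in flare rates between tofacitinib and placebo" and a placebo flare rate of 57%.

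**The concern.** The design withdraws active treatment from half of the responders, so more flares are expected on placebo. Under 8.3 each of those flares is a worsening of the underlying disease and can be recorded as an AE. The double-blind AE percentages would then partly restate the primary endpoint, with the sign favouring tofacitinib.

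At stake is the arm comparison of overall AEs. A real excess of other AEs on tofacitinib could be shrunk, hidden or reversed. Because 6.9.1 and 8.13 can each be applied to the same flare, two sites could also code one event differently and both comply. That would add noise to the AE-discontinuation table.

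**Working it through.** **Inputs from the documents (Protocol 9.1).** Placebo flare rate 0.57; difference 0.31, so tofacitinib 0.57 − 0.31 = 0.26. About 170 polyarticular subjects enrolled, 54% to 65% randomised 1:1, which gives 170 × 0.54 / 2 = 45.9 to 170 × 0.65 / 2 = 55.25 per arm.

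**Assumed, because the documents give no figure.** Non-flare AE risk b, equal in both arms, 20% to 80%. Share s of flares recorded as AEs, 10% to 100%. Independence of flare and other AEs.

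**Step 1: the plan's own figure.** The protocol claims "a power of approximately 90% or above" with "a 2-sided 5% Type I error". Using the unpooled normal approximation:
- At 45.9 per arm, the standard error is √((0.57×0.43 + 0.26×0.74)/45.9) = 0.0976. Then 0.31/0.0976 − 1.96 = 1.215, so power is 88.8%.
- At 55.25 per arm, power is 93.6%.
- Pooled variance gives 86.7% and 92.2%.

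The unpooled version reproduces the statement to within about a point at the low end. This confirms 57% and 26% as the working rates; the sample size is not disputed here.

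**Step 2: any-AE with equal non-flare risk.** Observed proportion = 1 − (1 − b)(1 − s × flare rate). The gap is (1 − b) × s × 0.31. Cells show placebo vs tofacitinib in %, with the gap in points.

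| b | s = 100% | s = 50% | s = 25% | s = 10% |
|---|---|---|---|---|
| 20% | 65.6 vs 40.8 (24.8) | 42.8 vs 30.4 (12.4) | 31.4 vs 25.2 (6.2) | 24.6 vs 22.1 (2.5) |
| 40% | 74.2 vs 55.6 (18.6) | 57.1 vs 47.8 (9.3) | 48.6 vs 43.9 (4.7) | 43.4 vs 41.6 (1.9) |
| 60% | 82.8 vs 70.4 (12.4) | 71.4 vs 65.2 (6.2) | 65.7 vs 62.6 (3.1) | 62.3 vs 61.0 (1.2) |
| 80% | 91.4 vs 85.2 (6.2) | 85.7 vs 82.6 (3.1) | 82.9 vs 81.3 (1.6) | 81.1 vs 80.5 (0.6) |

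The true difference is zero in every cell. With s = 100%, flare-derived AEs number 46 × 0.57 = 26.2 vs 46 × 0.26 = 12.0, or 55 × 0.57 = 31.4 vs 55 × 0.26 = 14.3. That is 14 to 17 more on placebo.

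**Step 3: masking.** The tofacitinib excess that would be exactly cancelled is (1 − b) × [1 − (1 − 0.57s)/(1 − 0.26s)], for b = 20%, 40%, 60% and 80%:
- s = 100%: 33.5, 25.1, 16.8 and 8.4 points.
- s = 50%: 14.3, 10.7, 7.1 and 3.6 points.
- s = 25%: 6.6, 5.0, 3.3 and 1.7 points.

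Example: a true 10-point excess (50% tofacitinib, 40% placebo) appears as 63.0% vs 74.2% at s = 100% (reversed), 56.5% vs 57.1% at s = 50% (hidden), and 53.2% vs 48.6% at s = 25% (about halved).

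**Step 4: the opposing effect of exposure.** Flare stops treatment, so placebo subjects are observed for less time. With constant flare hazards h = −ln(1 − flare rate)/26, the values are 0.0325 and 0.0116 per week. Mean double-blind exposure is (flare rate)/h = 17.6 weeks on placebo and 22.5 on tofacitinib.

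Take an equal non-flare hazard a = ln 2/26 = 0.0267 per week (50% risk over 26 weeks), with observation ending at flare. The crude non-flare proportion is a/(a + h) × [1 − exp(−26(a + h))]:
- Placebo: 0.451 × 0.785 = 35.4%.
- Tofacitinib: 0.697 × 0.630 = 43.9%.

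Removing flares from crude percentages therefore creates a spurious 8.5 points against tofacitinib. With all flares included, the same model gives 78.5% vs 63.0%, so the flare artefact dominates at s = 100%. First events per unit of time at risk recover the equal hazard a in both arms.

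**The case against.** The strongest points on the other side:

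- **Flare may seldom be recorded as an AE.** It is a derived composite confirmed centrally. Where the protocol wants a disease finding reported as an AE, it says so, as for new or worsening uveitis (7.2.3) and significant changes on targeted examination (7.2.2). Section 7.1.7 has no such instruction. This stands as a limit on size: the recorded share is unknown, and at 10% the artefact is small. It is not an exemption, since 8.3 and 8.1 are general.
- **AE withdrawals.** A reader might infer that every flare stop is counted as an AE withdrawal, with a difference of up to 31 points. The documents do not say so. Section 6.9.1 gives flare a separate route, and 8.13 only makes the AE coding possible.
- **SAEs.** A reader might infer that flare will drive the SAE percentages. A flare is an SAE only if it meets a criterion in 8.7, and no admission rate is given.
- **The rates are imperfect.** 57% and 26% are polyarticular planning values. Under 9.2.1 the endpoint also counts most other discontinuations as flare, so true flares may be fewer and an AE withdrawal could be counted twice in the model. The safety tables add ERA and PsA, for which no flare rate is given.
- **Important risks are analysed separately.** SAP 6.6.1 uses incidence rates for serious infections, malignancy and other named events. JIA flare is not among them.
- **Not everything is visible.** AE tables follow sponsor standards that are not reproduced, and text after 6.6.1 is redacted. A flare-excluded table may exist there.

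All of these narrow the point. None removes the route from 8.3 into the overall AE totals.

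**Conclusion.** The point holds in limited form. Read literally, the plan lets its efficacy outcome into the double-blind overall AE totals, and conditionally into the SAE and AE-discontinuation tables. At the planning rates, with equal non-flare risk of 20% to 80%, the artefact against placebo is about 6 to 25 points if every flare is recorded and about 1 to 3 points if 10% are. It can mask or reverse a moderate tofacitinib excess in those totals.

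These sizes rest on the assumed recording share, the assumed background risk, independence of flare and other AEs, and polyarticular planning rates that may overstate true flares.

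A reader might infer that tofacitinib's specific risks would be hidden. The documents do not support that: the special-interest incidence rates gain no flare events, and the whole-study exposure summary makes no comparison. Nor would crude flare-excluded percentages be a fair replacement, as Step 4 shows.

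**What to change.** 1. In SAP 6.6.1, present double-blind AEs, SAEs and AEs leading to discontinuation both with and without a list of JIA flare and worsening terms that is fixed before unblinding.
2. Give the flare-excluded comparison as exposure-adjusted incidence rates beside the crude percentages. SAP 6.6.1 already uses incidence rates for special-interest events.
3. Reconcile Protocol 6.9.1 and 8.13 so that a CCC-confirmed flare takes one discontinuation reason, disease flare, at all sites. A flare that is itself an SAE is still reported as an SAE and stays in the tables that include flare.

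The cost is a term list, a few extra tables and one instruction to sites. If few flares are recorded as AEs, the paired tables will nearly agree and little is lost.

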#### **8.4. Medication Errors**

Medication errors may result, in this study, from the administration or consumption of the wrong product, by the wrong subject, at the wrong time, or at the wrong dosage strength. Such medication errors occurring to a study participant are to be captured on the medication error case report form (CRF) which is a specific version of the adverse event (AE) page, and on the SAE form when appropriate. In the event of medication dosing error, the sponsor should be notified immediately.

Medication errors are reportable irrespective of the presence of an associated AE/SAE, including:

- Medication errors involving subject exposure to the investigational product;
- Potential medication errors or uses outside of what is foreseen in the protocol that do or do not involve the participating subject.

Whether or not the medication error is accompanied by an AE, as determined by the investigator, the medication error is captured on the medication error version of the adverse event (AE) page and, if applicable, any associated AE(s) are captured on an AE CRF page.

##### **8.4.1. Tofacitinib Overdose**

There is no experience with overdose of tofacitinib (CP-690,550). Pharmacokinetic data up to and including a single dose of 100 mg in healthy adult volunteers indicates that more than 95% of the administered dose is expected to be eliminated within 24 hours. There is no specific antidote for overdose with tofacitinib. In case of an overdose, it is recommended that the subject be monitored for signs and symptoms of adverse reactions. Subjects who develop adverse reactions should receive appropriate medical treatment.

Concomitant treatment with prohibited potent CYP3A inhibitors ([Appendix 4](#)) is assumed to result in a doubling of tofacitinib exposure. For further details, please refer to the SRSD (eg, the Investigator Brochure).

#### **8.5. Infections**

All treated infections occurring during the study, including, but not limited to, respiratory infections, cutaneous infections, urinary tract infections and episodes of suspicious or febrile diarrhea should be cultured and any identified organisms noted in the case report form.

Infections should be classified as either serious infections and/or treated infections, as defined below.

#### **8.5.1. Serious Infections**

A serious infection is any infection that requires hospitalization for treatment or requires parenteral antimicrobial therapy or meets other criteria that require it to be classified as a serious adverse event. A subject who experiences a serious infection must be discontinued from the study. This infection must be reported as a serious adverse event and should be listed as the reason for discontinuation in the CRF. Appropriate laboratory investigations, including but not limited to cultures should be performed to establish the etiology of any serious infection. All adverse events, including serious adverse events, must be reported as described in [Section 8.1](#) on [ADVERSE EVENT REPORTING](#).

#### **8.5.2. Treated Infections**

A treated infection is any infection that requires antimicrobial therapy by any route of administration or any surgical intervention (eg, incision and drainage). A subject who experiences a serious infection must be discontinued from the study. This information must be noted in the eCRF.

#### **8.6. Abnormal Test Findings**

The criteria for determining whether an abnormal objective test finding should be reported as an AE are as follows:

- Test result is associated with accompanying symptoms; and/or
- Test result requires additional diagnostic testing or medical/surgical intervention; and/or
- Test result leads to a change in study dosing or discontinuation from the study, significant additional concomitant drug treatment, or other therapy; and/or
- Test result is considered to be an AE by the investigator or sponsor.

Merely repeating an abnormal test, in the absence of any of the above conditions, does not constitute an AE. Any abnormal test result that is determined to be an error does not require reporting as an AE.

#### **8.7. Serious Adverse Events**

A serious adverse event is any untoward medical occurrence at any dose that:

- Results in death;
- Is life-threatening (immediate risk of death);
- Requires inpatient hospitalization or prolongation of existing hospitalization;

- Results in persistent or significant disability/incapacity (substantial disruption of the ability to conduct normal life functions);
- Results in congenital anomaly/birth defect.

Medical and scientific judgment is exercised in determining whether an event is an important medical event. An important medical event may not be immediately life-threatening and/or result in death or hospitalization. However, if it is determined that the event may jeopardize the subject or may require intervention to prevent one of the other AE outcomes, the important medical event should be reported as serious.

Examples of such events are intensive treatment in an emergency room or at home for allergic bronchospasm; blood dyscrasias or convulsions that do not result in hospitalization; or development of drug dependency or drug abuse.

#### **8.7.1. Protocol-Specified Serious Adverse Events**

There are no protocol-specified SAEs in this study. All SAEs will be reported by the investigator as described in previous sections and will be handled as SAEs in the safety database (see [Section 8.15.1](#) SAE Reporting Requirements).

#### **8.7.2. Potential Cases of Drug-Induced Liver Injury**

Abnormal values in aspartate aminotransferase (AST) and/or alanine aminotransferase (ALT) levels concurrent with abnormal elevations in total bilirubin level that meet the criteria outlined below in the absence of other causes of liver injury are considered potential cases of drug-induced liver injury (potential Hy's law cases) and should always be considered important medical events.

The threshold of laboratory abnormalities for a potential case of drug-induced liver injury depends on the subject's individual baseline values and underlying conditions. Subjects who present with the following laboratory abnormalities should be evaluated further to definitively determine the etiology of the abnormal laboratory values:

- Subjects with AST or ALT and total bilirubin baseline values within the normal range who subsequently present with AST or ALT values  $\geq 3$  times the upper limit of normal (X ULN) concurrent with a total bilirubin value  $\geq 2$  X ULN with no evidence of hemolysis and an alkaline phosphatase value  $\leq 2$  X ULN or not available.
- For subjects with preexisting ALT **OR** AST **OR** total bilirubin values above the ULN, the following threshold values should be used in the definition mentioned above:
  - For subjects with preexisting AST or ALT baseline values above the normal range: AST or ALT values  $\geq 2$  times the baseline values and  $\geq 3$  X ULN, or  $\geq 8$  X ULN (whichever is smaller).

Concurrent with

- For subjects with preexisting values of total bilirubin above the normal range: Total bilirubin level increased from baseline by an amount of at least 1 X ULN **or** if the value reaches  $\geq 3$  X ULN (whichever is smaller).

The subject should return to the investigational site and be evaluated as soon as possible, preferably within 48 hours from awareness of the abnormal results. This evaluation should include laboratory tests, detailed history, and physical assessment.

In addition to repeating measurements of AST and ALT, laboratory tests should include albumin, creatine kinase, total bilirubin, direct and indirect bilirubin, gamma-glutamyl transferase, prothrombin time (PT)/ international normalized ratio (INR), and alkaline phosphatase. A detailed history, including relevant information, such as review of ethanol, acetaminophen, recreational drug and supplement consumption, family history, occupational exposure, sexual history, travel history, history of contact with a jaundiced person, surgery, blood transfusion, history of liver or allergic disease, and work exposure, should be collected. Further testing for acute hepatitis A, B, or C infection and liver imaging (eg, biliary tract) may be warranted. All cases confirmed on repeat testing as meeting the laboratory criteria defined above, with no other cause for liver function test (LFT) abnormalities identified at the time, should be considered potential Hy's law cases irrespective of availability of all the results of the investigations performed to determine etiology of the abnormal LFTs. Such potential Hy's law cases should be reported as SAEs.

### **8.8. Hospitalization**

Hospitalization is defined as any initial admission (even less than 24 hours) in a hospital or equivalent healthcare facility or any prolongation of an existing admission. Admission also includes transfer within the hospital to an acute/intensive care unit (eg, from the psychiatric wing to a medical floor, medical floor to a coronary care unit, or neurological floor to a tuberculosis unit). An emergency room visit does not necessarily constitute a hospitalization; however, the event leading to the emergency room visit should be assessed for medical importance.

Hospitalization does not include the following:

- Rehabilitation facilities;
- Hospice facilities;
- Respite care (eg, caregiver relief);
- Skilled nursing facilities;
- Nursing homes;
- Same-day surgeries (as outpatient/same-day/ambulatory procedures).

Hospitalization or prolongation of hospitalization in the absence of a precipitating, clinical AE is not in itself an SAE. Examples include:

- Admission for treatment of a preexisting condition not associated with the development of a new AE or with a worsening of the preexisting condition (eg, for workup of persistent pre-treatment laboratory abnormality);
- Social admission (eg, subject has no place to sleep);
- Administrative admission (eg, for yearly physical examination);
- Protocol-specified admission during a study (eg, for a procedure required by the study protocol);
- Optional admission not associated with a precipitating clinical AE (eg, for elective cosmetic surgery);
- Hospitalization for observation without a medical AE;
- Preplanned treatments or surgical procedures. These should be noted in the baseline documentation for the entire protocol and/or for the individual subject.

Diagnostic and therapeutic noninvasive and invasive procedures, such as surgery, should not be reported as AEs. However, the medical condition for which the procedure was performed should be reported if it meets the definition of an AE. For example, an acute appendicitis that begins during the AE reporting period should be reported as the AE, and the resulting appendectomy should be recorded as treatment of the AE.

